2. SYNOPSIS

Name of Sponsor: Alexion Pharmaceuticals, Inc. Name of Investigational Product: ALXN1210 Name of Active Ingredient: ALXN1210 Title of Study: A Phase 1 Study to Evaluate the Safety, Tolerability, Pharmacokinetics, Pharmacodynamics, and Immunogenicity of a Single Dose of ALXN1210 Administered Subcutaneously Compared to Intravenously in Healthy Subjects (Protocol ALXN1210-SC-101) EudraCT Number: 2016-001617-24 Study Center: This study will be conducted by Richmond Pharmacology Ltd. at the following facility:		
Name of Investigational Product: ALXN1210 Name of Active Ingredient: ALXN1210 Title of Study: A Phase 1 Study to Evaluate the Safety, Tolerability, Pharmacokinetics, Pharmacodynamics, and Immunogenicity of a Single Dose of ALXN1210 Administered Subcutaneously Compared to Intravenously in Healthy Subjects (Protocol ALXN1210-SC-101) EudraCT Number: 2016-001617-24 Study Center:		
ALXN1210 Name of Active Ingredient: ALXN1210 Title of Study: A Phase 1 Study to Evaluate the Safety, Tolerability, Pharmacokinetics, Pharmacodynamics, and Immunogenicity of a Single Dose of ALXN1210 Administered Subcutaneously Compared to Intravenously in Healthy Subjects (Protocol ALXN1210-SC-101) EudraCT Number: 2016-001617-24 Study Center:		
Name of Active Ingredient: ALXN1210 Title of Study: A Phase 1 Study to Evaluate the Safety, Tolerability, Pharmacokinetics, Pharmacodynamics, and Immunogenicity of a Single Dose of ALXN1210 Administered Subcutaneously Compared to Intravenously in Healthy Subjects (Protocol ALXN1210-SC-101) EudraCT Number: 2016-001617-24 Study Center:		
ALXN1210 Title of Study: A Phase 1 Study to Evaluate the Safety, Tolerability, Pharmacokinetics, Pharmacodynamics, and Immunogenicity of a Single Dose of ALXN1210 Administered Subcutaneously Compared to Intravenously in Healthy Subjects (Protocol ALXN1210-SC-101) EudraCT Number: 2016-001617-24 Study Center:		
Title of Study: A Phase 1 Study to Evaluate the Safety, Tolerability, Pharmacokinetics, Pharmacodynamics, and Immunogenicity of a Single Dose of ALXN1210 Administered Subcutaneously Compared to Intravenously in Healthy Subjects (Protocol ALXN1210-SC-101) EudraCT Number: 2016-001617-24 Study Center:		
Immunogenicity of a Single Dose of ALXN1210 Administered Subcutaneously Compared to Intravenously in Healthy Subjects (Protocol ALXN1210-SC-101) EudraCT Number: 2016-001617-24 Study Center:		
Healthy Subjects (Protocol ALXN1210-SC-101) EudraCT Number: 2016-001617-24 Study Center:		
EudraCT Number: 2016-001617-24 Study Center:		
Study Center:		
This study will be conducted by Richmond Tharmacology Ltd. at the following facility.		
Croydon University Hospital (Woodcroft Wing)		
[name]		
[name]		
[name]		
United Kingdom		
-		
Telephone: PPD		
Length of Study: Phase of Development: 1		
Estimated date first subject enrolled: September 2016		
Estimated date last subject completed: February 2017		
Study Rationale:		
The purpose of the study is to evaluate the safety, tolerability, pharmacokinetics (PK), pharmacodynamics (PD),		
and immunogenicity of a single dose of ALXN1210 administered subcutaneously (SC) compared to a single dose		
of ALXN1210 administered intravenously (IV) in healthy subjects. Data from this study will be used to determine		
the absolute bioavailability of ALXN1210 SC in healthy subjects.		
ALXN1210 is a humanized monoclonal antibody (mAb) that inhibits terminal complement. It specifically binds		
the human complement protein C5 thereby inhibiting its cleavage to C5a and C5b during complement activation.		
This inhibition not only prevents the release of the proinflammatory mediator C5a, but also inhibits the formation of the cytolytic pore-forming membrane attack complex (MAC) terminal complement complex (C5b-9). The		
mechanism of action described here provides a rationale for the potential therapeutic use of ALXN1210 in diseases		
where complement activation is involved (eg, paroxysmal nocturnal hemoglobinuria [PNH] or atypical hemolytic uremic syndrome [aHUS]).		
dreinie syndrome [arros]).		
ALXN1210 has been administered safely to healthy subjects in 200-mg and 400-mg IV doses in a single ascending		
dose (SAD) study (Study ALXN1210-HV-101; $N = 10$). Healthy subjects have also been administered multiple		
400-mg and 800-mg IV doses on an every 4 week (Q4W) regimen in an ongoing multiple ascending dose (MAD)		
study (Study ALXN1210-HV-102; $N = 12$). The starting doses of ALXN1210 IV in the 2 healthy volunteer studies		
were selected to assess safety and tolerability in healthy volunteers and to have measurable pharmacologic activity		
(eg, inhibition of complement activation). In addition, administration of multiple doses of ALXN1210 IV to		
25 patients with PNH has been safe and tolerated, to date, at single doses up to 2000 mg.		
Objectives:		
The primary objectives of this study are as follows:		
• To evaluate the safety and tolerability of a single dose of ALXN1210 SC compared to ALXN1210 IV in		
healthy subjects, as assessed by physical examination findings, vital sign measurements, immunogenicity,		
laboratory analysis, and assessments of adverse events (AEs).		
• To determine the absolute bioavailability of ALXN1210 SC.		

[figure not shown]
The secondary objective of the study is as follows:

• To evaluate the PD effects of ALXN1210 SC compared to ALXN1210 IV, as assessed by the level of free C5 and chicken red blood cell (cRBC) hemolysis.

Study Design and Methodology:

This is a Phase 1 study designed to evaluate the safety, tolerability, PK, PD, and immunogenicity of a single 400-mg dose of ALXN1210 SC compared to a single 400-mg dose of ALXN1210 IV or placebo SC in 42 healthy subjects. All subjects will be screened for eligibility in the study after providing signed and dated institutional ethics committee-approved written informed consent to participate and before any study-specific screening procedures are performed.

Six subjects will initially be randomly assigned in a 2:1 ratio to Cohort 1a, in a blinded fashion, to receive either a single 400-mg dose of ALXN1210 SC or single dose of placebo SC. The Safety Review Committee (SRC) will evaluate the first 48 hours of post-dose clinical safety data for subjects in Cohort 1a before enrollment into Cohorts 1b or 2 may begin. Thirty-six subjects will then be randomly assigned, in a 2:1 ratio, to either Cohort 1b (N=24) or Cohort 2 (N=12). Within Cohort 1b, the 24 subjects will further be randomly assigned, in a 5:1 ratio and blinded fashion, to receive either a single 400-mg dose of ALXN1210 SC or a single dose of placebo SC, respectively. The 12 subjects in Cohort 2 will receive a single 400-mg dose of ALXN1210 IV in an open-label fashion.

Abbreviations: A = active drug; IV = intravenous; P = placebo; SC = subcutaneous; SRC = Safety Review Committee Note: The SRC will review the first 48 hours of post-dose safety data from Cohort 1a before enrollment into Cohorts 1b or 2 may begin.

At the sponsor's discretion, up to 8 additional subjects (2 subjects each in Cohorts 1a and 1b and 4 subjects in Cohort 2) may be enrolled into the study if 2 or more subjects discontinue within 3 months for reasons other than drug-related AEs, and after consultation with the SRC. All enrolled subjects will be included in analyses as appropriate. Subjects in Cohorts 1a and 1b will be combined for analyses. Subjects who withdraw from the study subsequent to dosing will be followed for safety assessments through the last scheduled study visit, if possible.

Subjects will participate in the study for up to 39 weeks, including a screening period of up to 70 days, followed by a 200day follow-up period for safety, PK, PD, and immunogenicity assessments after study drug administration.

Number of subjects (planned):

Forty-two subjects are planned for evaluation of the primary and secondary objectives in this study: 6 (4 ALXN1210 SC, 2 placebo SC) subjects in Cohort 1a; 24 (20 ALXN1210 SC, 4 placebo SC) subjects in Cohort 1b, and 12 (ALXN1210 IV) subjects in Cohort 2. See the synopsis section "Study Design and Methodology" regarding addition of subjects who withdraw or are withdrawn from the study after dosing.

Diagnosis and main criteria for inclusion:

All subjects must meet the following inclusion and exclusion criteria. Subjects who fail to meet eligibility criteria may not be rescreened for participation in the study, unless the condition that led to eligibility failure is transient, self-limited, and easily treatable, and is expected to be resolved at the time of dosing, as agreed by the investigator and medical monitor.

Inclusion:

- 1. Healthy subjects, aged 25 through 55 years, inclusive, at the time of dosing.
- 2. Body mass index (BMI) from 18 through 29.9 kg/m², inclusive, and weight between 50 and 100 kg, inclusive.
- 3. QT interval corrected using the Fridericia's formula $(QTcF) \le 450$ msec for males and ≤ 470 msec for females at screening and prior to dosing on Day 1.
- 4. Willing and able to give written informed consent and comply with the study visit schedule.
- 5. Documented vaccination with a tetravalent meningococcal conjugate vaccine (MCV4) at least 56 days and not more than 3 years prior to dosing. Documentation must include a positive serum bactericidal antibody (SBA) titer to confirm an immune response before study drug administration.
- 6. Vaccination with serogroup B meningococcal vaccine at least 56 days prior to dosing on Day 1, with a booster administered at least 28 days prior to dosing on Day 1, with at least 28 days between the first and second injections.
- 7. Female subjects of childbearing potential, if heterosexually active, must use highly effective or acceptable contraception as defined below, starting at screening and continuing until at least 6 months after study drug administration. Antibiotic prophylaxis is required during this study, which can compromise the efficacy of hormonal contraception. Therefore, it is recommended that subjects using hormonal contraception also use barrier contraception (eg, condom or diaphragm with spermicide) for the duration of antibiotic prophylaxis.

Highly effective contraceptive methods for females are as follows:

- Combined (estrogen- and progestogen-containing) hormonal contraception associated with inhibition of ovulation as follows:
 - Oral
 - Intravaginal
 - Transdermal
- Progestogen-only hormonal contraception associated with inhibition of ovulation as follows:
 - Oral
 - Injectable
 - Implantable
- Intrauterine device
- Intrauterine hormone-releasing system
- Bilateral tubal occlusion

Male subjects, if heterosexually active and with a female spouse or partner of childbearing potential or a pregnant or breastfeeding spouse or partner, must agree to use barrier contraception (male condom) for the treatment period and for at least 6 months after study drug administration. Barrier contraception is required even with documented medical assessment of surgical success of a vasectomy. Female spouses or partners of male subjects who are of childbearing potential must use highly effective contraception as defined above, or acceptable contraception as defined below, starting at screening and continuing until at least 6 months after study drug administration. Male subjects must not donate sperm during the screening and treatment periods and for at least 6 months after study drug administration.

Acceptable contraceptive methods are as follows:

• Simultaneous use of male condom and, for the female partner, occlusive cap (diaphragm or cervical/vault caps) with intravaginally applied spermicide

Exclusion:

- 1. Subjects who are in intimate and prolonged contact with (defined as living under the same roof or providing personal care to) people younger than 2 years of age or older than 65 years of age, or who are either immunocompromised or have one of the following underlying medical conditions: anatomic or functional asplenia (including sickle cell disease); congenital complement, properdin, factor D, or primary antibody deficiencies; acquired complement deficiencies (eg, those receiving eculizumab); or human immunodeficiency virus (HIV).
- 2. Subjects who are one of the following:
 - Professionals who are exposed to environments of greater risk for meningococcal disease
 - Research, industrial, and clinical laboratory personnel who are routinely exposed to *N meningitidis*
 - Military personnel during recruit training (military personnel may be at increased risk of meningococcal infection when accommodated in close quarters)
 - Daycare center workers
 - Those living on a college or university campus
 - Those who plan to travel during the course of the study to or have travelled to endemic areas for meningococcal meningitis (eg, India, Sub-Saharan Africa, pilgrimage to Saudi Arabia for Hajj) within 6 months prior to dosing
- 3. History of any *Neisseria* infection.
- 4. History of unexplained, recurrent infection, or infection requiring treatment with systemic antibiotics within 90 days prior to dosing.
- 5. HIV infection (evidenced by HIV-1 or HIV-2 antibody titer).
- 6. Acute or chronic hepatitis B virus (HBV) infection. Hepatitis B surface antigen (HBsAg) testing is required for all subjects prior to enrollment. Subjects with positive HBsAg will not be enrolled. For subjects with negative HBsAg, the following testing algorithm will be required:
 - If hepatitis B core antibody (HBcAb) is negative, the subject is eligible to enroll;
 - If HBcAb is positive, the hepatitis B surface antibody (HBsAb) will be tested.
 - If both HBcAb and HBsAb are positive, the subject is eligible to enroll.
 - If HBcAb is positive and HBsAb is negative, the subject will not be enrolled.
- 7. Acute or chronic hepatitis C virus (HCV) infection (evidenced by antibody titer).
- 8. Active systemic viral or fungal infection within 14 days prior to dosing.
- 9. Positive or indeterminate QuantiFERON[®]-TB test indicating possible tuberculosis (TB) infection.
- 10. History of latent or active TB or exposure to endemic areas within 8 weeks prior to the screening visit.
- 11. Female subjects who are breastfeeding or are heterosexually active and unwilling to practice contraception and are not postmenopausal. Postmenopausal is defined as amenorrhea ≥ 12 consecutive months without another cause and a documented serum follicle-stimulating hormone level ≥ 40 mIU/mL and estradiol concentration ≤ 110 pmol/L within the 6 months prior to study drug administration.
- 12. Positive serum pregnancy test at screening or on Day -1.
- 13. Serum creatinine greater than the upper limit of normal (ULN) of the reference range of the testing laboratory at screening or on Day -1.
- 14. Alanine aminotransferase (ALT) or aspartate aminotransferase (AST) > ULN of the reference range of the testing laboratory at screening or > $1.5 \times$ ULN of the reference range of the testing laboratory on Day -1.
- 15. Any of the following hematology results: hemoglobin < 130 g/L for males and < 115 g/L for females, hematocrit < 0.37 L/L for males and < 0.33 L/L for females, white blood cell (WBC) count < $3.0 \times 10^{3}/\mu$ L, absolute neutrophil count < $2.0 \times 10^{3}/\mu$ L, and platelet count < 150 or > 400 × $10^{3}/\mu$ L at screening or on Day –1. Complete blood count (CBC) clinical laboratory results that are considered clinically relevant and unacceptable by the investigator on Day –1.
- 16. History of complement deficiency or complement activity below normal reference range as evaluated by complement alternative pathway (CAP) ELISA at screening.
- 17. History of malignancy with the exception of a nonmelanoma skin cancer or carcinoma in situ of the cervix that has been treated with no evidence of recurrence.
- 18. Participation in a clinical study within 30 days before initiation of dosing on Day 1 or use of any

experimental small-molecule therapy within 30 days prior to dosing on Day 1.

- 19. Participation in more than one clinical study of an mAb, or participation in a clinical study of an mAb within the 12 months prior to screening, during which the subject was exposed to the active study drug. Subjects who have participated in only one study of an mAb may be considered for enrollment if they completed that study more than 12 months prior to screening.
- 20. Prior exposure to ALXN1210.
- 21. Major surgery or hospitalization within 90 days prior to dosing.
- 22. History of allergy to excipients of ALXN1210 (eg, polysorbate 80).
- 23. Documented history of allergy to penicillin or cephalosporin.
- 24. History of significant allergic reaction (eg, anaphylaxis or angioedema) to any product (food, pharmaceutical, etc).
- 25. Currently smokes > 10 cigarettes daily (former smokers may be permitted to enroll at the investigator's discretion).
- 26. History of illicit drug abuse, history of significant alcohol abuse within 1 year prior to the screening visit, or regular use of alcohol within 6 months prior to the screening visit (more than 14 units of alcohol per week [1 unit = 150 mL of wine, 360 mL of beer, or 45 mL of 40% alcohol]).
- 27. Positive urine drug toxicology screen at screening or on Day 1.
- 28. Alcohol consumption within 48 hours prior to study drug administration or positive alcohol breath test on Day -1.
- 29. Donation of plasma within 7 days prior to dosing. Donation or loss (excluding volume drawn at screening) of more than 50 mL of blood within 30 days prior to dosing or more than 499 mL of blood within 56 days prior to dosing.
- 30. History of continuous topical, inhaled, or systemic steroid use > 28 days or history of any inhaled or topical immunosuppressive therapy within 90 days prior to study drug administration.
- 31. Use of prescription medications (excluding oral contraceptives) within 14 days prior to study drug administration, except with prior approval of the sponsor.
- 32. Regular use of nonprescription, over-the-counter medications, including herbal remedies and supplements, within 14 days prior to study drug administration. Multivitamins, acetaminophen ≤ 2 g per day, and topical skin products without significant systemic absorption are allowed.
- 33. Clinical diagnosis of any autoimmune or rheumatologic disease (eg, systemic lupus erythematosus, rheumatoid arthritis).
- 34. Immunization with a live-attenuated vaccine 28 days prior to dosing or planned vaccination during the course of the study (except for the vaccination planned by the study protocol). Immunization with inactivated or recombinant influenza vaccine is permitted.
- 35. Presence of fever (confirmed body temperature > 37.6°C) (eg, a fever associated with a symptomatic viral or bacterial infection) within 14 days prior to dosing.
- 36. Subjects with any medical history, conditions, or risks that, in the opinion of the investigator, may interfere with the subject's full participation in the study or compliance with the protocol, or may pose any additional risk for the subject or confound the assessment of the subject or outcome of the study.

Investigational product, dosage, and mode of administration:

ALXN1210 SC: ALXN1210 SC is formulated at pH 7.4 and each vial contains 100 mg of ALXN1210 in 50 mM sodium phosphate, 25 mM arginine, 5% sucrose, and 0.05% polysorbate 80. ALXN1210 SC is provided as a fully formulated, sterile, preservative-free, 100-mg/mL aqueous solution of ALXN1210 for SC administration and is supplied in 2-mL single-use vials. Each vial of ALXN1210 SC drug product includes a nominal overfill to ensure that 1 mL (100 mg of ALXN1210) can be withdrawn for administration. ALXN1210 SC will be administered SC as four 1-mL injections.

ALXN1210 IV: ALXN1210 IV is formulated at pH 7.0 and each vial contains 150 mg of ALXN1210 in 10 mM sodium phosphate, 150 mM sodium chloride, 0.02% polysorbate 80, and water for injection. ALXN1210 IV is provided as a fully formulated, sterile, preservative-free, 10-mg/mL aqueous solution of ALXN1210 and is supplied in 20-mL single-use vials. ALXN1210 IV will be administered by IV infusion at a maximum rate of 333 mL/hr, excluding interruption for safety or technical reasons.

Reference therapy, dosage, and mode of administration:

Placebo SC: Each dose of placebo SC contains 0.9% sodium chloride for injection, European Pharmacopoeia (Ph Eur) or British Pharmacopeia (BP), to the same volume as specified for Cohorts 1a and 1b.

Planned duration of treatment:

Screening period: up to 70 days

Dosing and observation periods: For Cohorts 1a and 1b, a single 400-mg dose of ALXN1210 SC or placebo SC (administered as four 100-mg SC injections) on Day 1, followed by an observation period of 200 days. For Cohort 2, a single 400-mg dose of ALXN1210 IV on Day 1, followed by an observation period of 200 days. Subjects will be followed for safety, PK, PD, and immunogenicity assessments.

Endpoints:

Safety:

Safety assessments will include physical examination findings, vital sign measurements, immunogenicity (antidrug antibody [ADA]) testing, laboratory evaluations, electrocardiogram (ECG) results, infusion site and injection site evaluations, and monitoring of AEs. Adverse events will be graded according to criteria from the National Cancer Institute Common Terminology Criteria for Adverse Events v4.03, published 14 Jun 2010. Laboratory evaluations will include hematology, chemistry, and coagulation panels; CBC with differential; urinalysis; and pregnancy testing for female subjects.

Pharmacokinetics and Pharmacodynamics:

- Serum concentrations of ALXN1210 will be assayed and serum samples for PD assays will be collected from the following sampling time points: pre-dose (within 15 minutes prior to start-of-infusion/injection [SOI]); Day 1 at end of infusion/injection (EOI), 30 minutes post EOI, and the following time points following SOI: 2 h, 4 h, and 8 h; Day 2 (24 h); Day 3 (48 h); Day 5 (96 h); Day 8 (168 h); Day 15 (336 h); Day 22 (504 h); Day 29 (672 h); Day 36 (840 h); Day 43 (1008 h); Day 50 (1176 h); Day 57 (1344 h); Day 71 (1680 h); Day 90 (2136 h); Day 120 (2856 h); Day 150 (3576 h); and Day 200 (4776 h).
- Using noncompartmental analysis methods, the serum concentrations data will be used to derive the following PK parameters: maximum observed serum concentration (C_{max}), time to maximum observed serum concentration (T_{max}), area under the serum concentration versus time curve from time zero to the last quantifiable concentration (AUC_t), AUC from time zero to infinity (AUC_{∞}), terminal elimination rate constant (λ_z), terminal elimination half-life (T_{V_2}), total clearance (CL or CL/F), and volume of distribution (V_d or V_d/F).

Immunogenicity:

• Serum samples will be collected at the following time points: pre-dose (within 15 minutes prior to SOI), and on Days 15 (336 h), 29 (672 h), 57 (1344 h), 90 (2136 h), 120 (2856 h), 150 (3576 h), and 200 (4776 h) and analyzed for ADA to ALXN1210.

The total anticipated volume of serum collected per subject for clinical laboratory, PK, PD, and immunogenicity assessments will not exceed 500 mL.

Statistical methods:

General:

A total evaluable sample size of 36 subjects, 24 ALXN1210 SC subjects from Cohort 1 and 12 ALXN1210 IV subjects from Cohort 2, will provide >80% power to infer that the lower bound of a 90% confidence interval for the ratio of the bioavailability of ALXN1210 SC to IV is > 0.4 assuming an absolute bioavailability of 0.6 and a coefficient of variation of 0.35. Additionally, 6 subjects will receive placebo SC, 2 in Cohort 1a and 4 in Cohort 1b. Randomization to Cohort 1a will be conducted in a 2:1 ratio, and Cohort 1b in a 5:1 ratio, to receive either ALXN1210 SC or placebo SC. This brings the total planned number of subjects to N=42.

In general, descriptive statistics for continuous variables will include number of nonmissing values, arithmetic mean, standard deviation, median, minimum, and maximum. Descriptive statistics for PK parameters will include number of observations, arithmetic mean, standard deviation, arithmetic coefficient of variation (%CV), median, minimum, maximum, geometric mean and geometric %CV. Categorical variables will be summarized using percentages and frequency counts, by cohort and time point.

Safety:

All subjects who received at least 1 dose of study drug will be included in the safety analysis. Safety data will be assessed using descriptive statistics. No inferential statistical analyses are planned on the safety parameters of this

study. Safety analysis will include an analysis of all AEs, laboratory values, ECGs, and vital sign measurements.

Shift tables will be produced for selected laboratory parameters. These tables will summarize the number of subjects with each baseline grade relative to the normal ranges and changes to the worst highest grade assessed post-dose during the study.

Pharmacokinetics/Pharmacodynamics:

Individual PK parameters (including descriptive statistics as follows: number of observations, arithmetic mean, standard deviation, arithmetic coefficient of variation [CV], median, minimum, maximum, geometric mean, and geometric CV) will be determined for the ALXN1210-treated subjects.

The PD effects of ALXN1210 SC and IV will be evaluated by assessing changes in serum total and free C5 concentrations, cRBC hemolysis, and other measures of C5 activation over time, using descriptive statistics.

Immunogenicity:

Immunogenicity, as measured by ADA, will be summarized in tabular form by cohort and by-subject listings.

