¹ Permissible windows for study assessments are described in the study operations manual. ² EOI will be approximately 15 minutes after SOI.

³ Subject will be discharged from CRU after completing all Day 5 assessments. Subjects will be provided a "Study Participant ID card" with information for Healthcare Provider and participant on symptoms of meningitis infection.

⁴ Signed and dated EC-approved ICF must be obtained before any study-specific screening procedures are performed.

⁵ For subjects who do not have adequate documentation of prior MCV4 immunization or serogroup B vaccination, MCV4 immunization will be performed at least 56 days prior to first dose on Day 1, and vaccination for serogroup B meningococcal infections will be administered at least 56 days prior to Day 1 dosing with a booster administered at least 28 days prior to dosing on Day 1.

⁶ Complement activity, confirmed by a suitable assay such as complement alternative pathway (CAP) ELISA/C5 (hemolysis) inhibition, will be performed at screening to confirm subjects do not have a complement deficiency.

⁷ The sample drawn on Day -1 will be stored for future analysis should the post-dose sample indicate that complement has not normalized.

⁸ Serum pregnancy test for all female subjects to confirm a female subject is not pregnant.

⁹ On Dav 1, vital sign measurements will be assessed pre-dose (within 15 minutes prior to SOI) and at EOI, 30 minutes after EOI, 2 hours after SOI, 4 hours after SOI, and 8 hours after SOI.

¹⁰On Day 1, triplicate 12-lead ECGs will be performed pre-dose and approximately 15 minutes post-EOI.

¹¹Continuous cardiac registration predose through duration of IV infusion (Cohort 2) and until 3 hours post SC injection (Cohorts 1a and 1b).

¹²Infusion or injection site evaluations will be done within 15 minutes of the start of infusion/injection and \pm 15 minutes of the other scheduled times on Day 1. Indurations or reactions < 1cm will not be listed as an adverse event unless it persists for more than 24 hr. Pain at site of infusion or injection will be assessed using a Visual Analog Scale (0-10). Pain will not be assessed pre-dose.

¹³The investigator or designee will meet with the subject at each visit to discuss the potential safety risks of ALXN1210, and to address any safety concerns on the part of the subject.

¹⁴Collection of AEs and SAEs will begin at ICF signing.

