10.2. Subject Exclusion Criteria

Subjects meeting any of the following exclusion criteria are not eligible to participate in the study:

- 1. Subjects who are in intimate and prolonged contact with (defined as living under the same roof or providing personal care to) people younger than 2 years of age or older than 65 years of age, or who are either immunocompromised or have one of the following underlying medical conditions: anatomic or functional asplenia (including sickle cell disease); congenital complement, properdin, factor D, or primary antibody deficiencies; acquired complement deficiencies (eg, those receiving eculizumab); or human immunodeficiency virus (HIV).
- 2. Subjects who are one of the following:
 - Professionals who are exposed to environments of greater risk for meningococcal disease
 - Research, industrial, and clinical laboratory personnel who are routinely exposed to *N meningitidis*
 - Military personnel during recruit training (military personnel may be at increased risk of meningococcal infection when accommodated in close quarters)
 - Daycare center workers
 - Those living on a college or university campus
 - Those who plan to travel during the course of the study to or have travelled to endemic areas for meningococcal meningitis (eg, India, Sub-Saharan Africa, pilgrimage to Saudi Arabia for Hajj) within 6 months prior to dosing
- 3. History of any Neisseria infection.

- 4. History of unexplained, recurrent infection, or infection requiring treatment with systemic antibiotics within 90 days prior to dosing.
- 5. HIV infection (evidenced by HIV-1 or HIV-2 antibody titer).
- 6. Acute or chronic hepatitis B virus (HBV) infection. Hepatitis B surface antigen (HBsAg) testing is required for all subjects prior to enrollment. Subjects with positive HBsAg will not be enrolled.

For subjects with negative HBsAg, the following testing algorithm will be required:

- If hepatitis B core antibody (HBcAb) is negative, the subject is eligible to enroll.
- If HBcAb is positive, the hepatitis B surface antibody (HBsAb) will be tested.
 - If both HBcAb and HBsAb are positive, the subject is eligible to enroll.
 - If HBcAb is positive and HBsAb is negative, the subject will not be enrolled.
- 7. Acute or chronic hepatitis C virus (HCV) infection (evidenced by antibody titer).
- 8. Active systemic viral or fungal infection within 14 days prior to dosing.

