11.2.2. Risk of Infection Reminders

Risk of infection will be explained and discussed with subjects during the informed consent process, occurring at the screening visit. In order to increase the risk awareness and promote quick disclosure of any potential signs or symptoms of infection experienced by the subjects during the course of the study, additional discussion and explanation of the potential risks, signs, and symptoms, as described in the informed consent form (ICF), will take place at specific time points throughout the study as noted in the Schedule of Assessments (Section 9). Subjects will also be provided a safety card to carry with them at all times.

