15.1.6.8. Tuberculosis

Serum samples for a QuantiFERON-TB test will be collected as described in the Schedule of Assessments (Section 9).

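### Exclusion 10 ends its TB-exposure look-back at the screening visit, so for anyone screened at Day -56 or earlier it covers none of the last 56 days before dosing

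*Protocol*

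**What the plan says.** Exclusion 10 appears in the same words in the Protocol Synopsis and in Section 10.2: "History of latent or active TB or exposure to endemic areas within 8 weeks prior to the screening visit". The exposure window is therefore counted backwards from screening, not from dosing.

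The Synopsis describes participation as "including a screening period of up to 70 days", and the screening column of Table 4 (Section 9) runs from Day -70 to Day -2. Three further statements fix how early some subjects must be screened:

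- Section 11.2.2 places consent at the screening visit: "during the informed consent process, occurring at the screening visit".
- Section 9, footnote 4 to Table 4: "Signed and dated EC-approved ICF must be obtained before any study-specific screening procedures are performed".
- Section 9, footnote 5 to Table 4. This applies "For subjects who do not have adequate documentation of prior MCV4 immunization or serogroup B vaccination". For them, "MCV4 immunization will be performed at least 56 days prior to first dose on Day 1", and the first serogroup B injection has the same 56-day minimum (also Section 11.2.1).

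On TB testing, Section 15.1.6.8 says only "Serum samples for a QuantiFERON-TB test will be collected as described in the Schedule of Assessments". The schedule marks the test in the screening column of Table 4. It is not marked on Day -1 and does not appear in Table 5. Medical history is likewise marked at screening only.

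Exclusion 2 in Section 10.2 does run to dosing, and also bars planned travel during the study. It is written for areas endemic for meningococcal meningitis: "eg, India, Sub-Saharan Africa, pilgrimage to Saudi Arabia for Hajj) within 6 months prior to dosing".

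**The concern.** The sponsor uses two TB safeguards together: a negative QuantiFERON test (exclusion 9) and no recent stay in an endemic area (exclusion 10). The protocol thus does not rely on the test alone for recent exposure. Yet the exposure rule stops at a visit that may be ten weeks before dosing, and nothing TB-specific is scheduled between a subject's test and dosing.

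Other infection and exposure rules in the same list look back from dosing: exclusion 2 (travel), 4 (infection needing systemic antibiotics), 8 (viral or fungal infection) and 35 (fever). Exclusions 12 to 15 (pregnancy and laboratory results) are checked at screening and again on Day -1. Exclusion 10 has neither feature.

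What is at stake is who may be dosed. A volunteer exposed in a TB-endemic area after screening remains eligible under exclusion 10 as worded. No estimate, power figure or analysis population depends on it.

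**Working it through.** **Inputs**

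| Input | Value | Source |
|---|---|---|
| Look-back length | 8 weeks = 56 days, ending at the screening visit | Synopsis and Section 10.2, exclusion 10 |
| Screening range | Day -70 to Day -2 | Table 4 |
| Minimum lead time if MCV4 or first serogroup B injection is given in-study | 56 days | Table 4 footnote 5; Section 11.2.1 |
| Screening visit relative to in-study vaccination | on or before it | Table 4 footnote 4; Section 11.2.2 |
| Follow-up | 200 days | Synopsis; Section 8.1 |

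**The plan's own figure.** (70 + 200) / 7 = 38.6 weeks, which rounds up to the stated 39 weeks. The timeline is being read as the protocol reads it.

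**Formulae.** Take Day -k as k days before Day 1, and let screening fall s days before dosing.

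- The look-back covers the stretch from s + 56 to s days before dosing.
- Days covered among the last 56 before dosing = max(0, 56 - s).
- The stretch before dosing that is not covered = s days.

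**Results**

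| Screening day | Window (days before dosing) | Covered, of last 56 | Not covered before dosing |
|---|---|---|---|
| -70 | 126 to 70 | 0 | 70 |
| -63 | 119 to 63 | 0 | 63 |
| -56 | 112 to 56 | 0 | 56 |
| -55 | 111 to 55 | 1 | 55 |
| -42 | 98 to 42 | 14 | 42 |
| -28 | 84 to 28 | 28 | 28 |
| -14 | 70 to 14 | 42 | 14 |
| -2 | 58 to 2 | 54 | 2 |

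Counting a Day 0 shifts each entry by at most one day and changes no conclusion.

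**Who falls where.** In-study vaccination (MCV4 or the first serogroup B injection) forces s to lie between 56 and 70, so coverage is 0 of 56 throughout. A subject with documentation of both vaccinations has no such minimum: s runs from 2 to 70 and coverage from 54 down to 0.

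**What else reaches the interval between screening and dosing.**

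- Exclusion 2 reaches it for meningococcal-endemic areas, with India, Sub-Saharan Africa and the Hajj as named examples.
- Exclusions 4, 8 and 35 reach it for illness, not for silent exposure.
- Exclusion 36 reaches it only through investigator judgement.
- The QuantiFERON test falls somewhere in Day -70 to Day -2, on a day the schedule does not fix.

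None of these is a TB-specific exposure rule.

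**The case against.** The strongest defence is that ending the exposure history at the stage where TB is tested is a coherent choice, and that no other passage contradicts it. The anchor is not unique either, since exclusions 19 and 26 also look back from screening. This stands as far as it goes: the point is a gap in coverage, not an inconsistency. It explains why the history should precede the test, but not why the later interval is left without a TB-specific exposure question.

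Four stronger readings are tempting, and the documents do not support them.

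- *The rule never covers the last 8 weeks.* This is true only for screening at Day -56 or earlier. At Day -2 it covers 54 of the 56 days.
- *The QuantiFERON sample is always drawn before vaccination.* Table 4 gives no order. Its screening column also holds vaccinations at Day -56 and Day -28 and the bactericidal titer, so the column is not one visit and the test could be drawn late.
- *Exposure four months before dosing excludes a subject while exposure two weeks before does not.* Four months is about 122 days, so the first half needs s + 56 to be at least 122, that is, screening at about Day -66 or earlier. At Day -56 the window reaches back only 112 days. The second half fails for travel already barred by exclusion 2.
- *The study drug raises TB risk.* Section 5.1.4.1 names encapsulated organisms, particularly *N meningitidis*. No passage links TB to complement inhibition or states the purpose of exclusion 10.

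Repeat physical examination on Day -1 and adverse-event monitoring from consent are partial safeguards. They would catch illness but not exposure.

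**Conclusion.** The point holds in limited form and is minor. For every subject given MCV4 or the first serogroup B injection in the study, and for anyone else screened at Day -56 or earlier, exclusion 10 covers 0 of the last 56 days before dosing. For documented, previously vaccinated subjects screened later it covers 1 to 54 of 56. Exposure between screening and dosing in a TB-endemic area outside the reach of exclusion 2 is addressed by no TB-specific rule, and the single QuantiFERON test is not repeated on Day -1.

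This rests on reading the screening visit as the consent visit, as Section 11.2.2 does. The documents do not say how many subjects would be vaccinated in-study, so the share with zero coverage could be anywhere from 0 to 100%. They also do not define TB-endemic areas, so the part of the gap that exclusion 2 leaves open cannot be sized. How long a TB look-back ought to be is a clinical matter and is not judged here.

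**What to change.** The sponsor should state whether the look-back is meant to stop at screening, and reconcile exclusion 10 with the dosing-anchored infection and exposure exclusions (2, 4, 8 and 35) so that the interval from screening to dosing is also covered. The simplest way is to leave the start where it is, 8 weeks before the screening visit, and move the end to dosing. That keeps the sponsor's 8-week figure and everything the rule now excludes. Simply recounting the 8 weeks from dosing would instead drop the earlier part of the present window for subjects screened early.

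The same change is needed in the Synopsis and in Section 10.2, and the exposure question should be re-asked at the existing Day -1 admission and marked in Table 4.

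The cost is one phrase in two places and one question at a visit that already takes place, carried in an amendment that needs the ethics approval described in Section 21.1. The downside is that an occasional volunteer who travels during screening will be excluded or deferred. Sample size and analyses do not change.
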